11.3.3 Subject Replacement

Subjects who do not complete at least two doses of BMSCs will be replaced in this study.

15-H-0088

[name].

Abbreviated Title: Early BMSC Pilot for Acute GVHD

Version Date: 6/16/2016

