3.4.2.4 Missed infusions

Unanticipated logistical challenges including, but not limited to, adverse weather, availability of transportation, or equipment-related delays may occur. Subjects can miss up to four (4) BMSC infusions in total over the course of the treatment protocol and remain enrolled and evaluable for response. If an infusion or series of infusions are missed, the infusion will not be rescheduled and the subject will go on to receive the next scheduled infusion in the treatment course. Subjects missing more than four (>4) BMSC infusions will be removed from the treatment protocol and will not be evaluable for the primary endpoint.

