8.3 TREATMENT LIMITING TOXICITIES

The observational period for determining Treatment Limiting Toxicities is from the initiation of the BMSC infusion to 3 weeks after the last infusion. A treatment related serious adverse event (TRSAE) is defined as an SAE which is at least probably or definitely related to the BMSC infusions. Any subject who encounters a TRSAE will not receive further infusions.

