9.1.1 Toxicity

Subjects experiencing BMSC infusion reaction as defined in Section 8.2 will receive no further BMSC infusions; subjects experiencing a grade 4 acute infusion reaction or hypersensitivity reaction will receive no further treatments; subjects experiencing a grade 3 acute infusion reaction or hypersensitivity reaction will receive no further treatments if symptoms do not resolve within 2 hours; subjects experiencing a grade 3 acute infusion reaction or hypersensitivity reaction will receive no further treatments if symptoms recur when infusion is restarted. Any subject who encounters a TRSAE will not receive further infusions. Subjects will be followed until off study criteria are met.

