11. BIOSTATISTICAL CONSIDERATIONS

11.1 PRIMARY ENDPOINT

The primary endpoint of this study is:

- The proportion of subjects reaching day +56 without a TRSAE.

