11.3.2 Sample Size

Let p be the probability of subjects reaching day +56 without a TRSAE. The sample size is determined by testing the null hypothesis $H_0 : p = 75\%$ versus the alternative hypothesis $H_a : p > 75\%$ with a one-sided significant level of 0.05. Based upon our previous phase 1 trial (12-H-0010), the TRSAE rate was 0 out of 10 subjects and we expect 95% subjects would reach day +56 without a TRSAE. Thus a sample size of 23 subjects will achieve 89.5% power to test the above hypotheses using an exact binomial test.

To account for the possibility of non-treatment related drop out, up to 2 additional subjects may be enrolled to replace those subjects that are non-evaluable for the study's primary endpoint for a total accrual of 25 patients. At an accrual rate of 1-2 subjects per month, this study will be completed in 12-18 months.

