11.3.4.2 For Safety

The trial will be monitored for safety based on Treatment Related Serious Adverse Events (TRSAE), which is also the primary endpoint of the study. A TRSAE is defined as an SAE which is at least probably or definitely related to the BMSC infusions. The trial will be stopped if 3 subjects have developed one or more TRSAE's. This is based on the binomial test of the primary hypothesis (Section 11.3.2) and at least 21 of 23 subjects without a TRSAE are needed to reject the null hypothesis. If 3 or more subjects developed TRSAE's are observed, the null hypothesis will not be rejected and we will stop the study early.

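### Section 11.3.3 replaces a subject whose infusions stopped after dose 1 because of a TRSAE, so the event can drop out of the primary safety proportion

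*Combined protocol and SAP*

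**What the plan says.** The primary endpoint (11.1) is "The proportion of subjects reaching day +56 without a TRSAE". Section 11.3.2 tests this proportion against 75% with 23 subjects, and 11.3.4.2 requires at least 21 of 23 without a TRSAE for rejection.

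Four rules decide who is in that proportion:

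- **Effect of a TRSAE on treatment (8.3, repeated in 9.1.1):** "Any subject who encounters a TRSAE will not receive further infusions".
- **Replacement (11.3.3):** "Subjects who do not complete at least two doses of BMSCs will be replaced in this study".
- **Extra places (11.3.2):** "up to 2 additional subjects may be enrolled to replace those subjects that are non-evaluable" for the primary endpoint, giving a total accrual of 25. The stated reason is drop-out unrelated to treatment.
- **Missed infusions (3.4.2.4):** "Subjects missing more than four (>4) BMSC infusions will be removed from the treatment protocol and will not be evaluable for the primary endpoint".

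Separately, the safety rule in 11.3.4.2 reads "The trial will be stopped if 3 subjects have developed one or more" TRSAEs. It refers to subjects and does not limit the count to evaluable ones.

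**The concern.** Put 8.3 and 11.3.3 together. A TRSAE that arises before the second dose is complete stops treatment, so the subject has fewer than two doses and is replaced. Because 11.3.2 ties replacement to non-evaluability, and 3.1.1 targets 23 evaluable subjects out of 25, the replaced subject can be taken out of the primary proportion. Nothing in the plan says that a subject stopped for a TRSAE stays in the denominator as a failure.

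The exclusion would then depend on the outcome being measured. In a single-arm trial whose primary endpoint is a safety proportion, that biases the estimate and its confidence interval towards safety. If replaced subjects were also left out of the three-subject count, the test itself would become too liberal.

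Section 3.4.2.4 could act in the same way if infusions withheld after a TRSAE counted as missed. That reading is weaker, because the section opens with logistical causes.

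**Working it through.** **Inputs.** From 11.3.2: null proportion 0.75, expected proportion 0.95, n = 23, one-sided level 0.05, stated power 89.5%, at most 2 replacements. From 11.3.4.2: reject with at least 21 of 23, stop at 3 subjects with a TRSAE. One quantity is not in the documents: the share *f* of TRSAEs that arise before the second dose is complete. I assume 1/8, 1/4 and 1/2 to show a range.

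**1. The plan's own figures.** With TRSAE probability q, the chance of at most 2 TRSAEs in 23 is Σ C(23,k) q^k (1−q)^(23−k) for k = 0, 1, 2.

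- q = 0.25: 0.0013 + 0.0103 + 0.0376 = 0.0492 (type I error).
- q = 0.05: 0.3074 + 0.3721 + 0.2154 = 0.8948 (power; stated 89.5%).

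The design reproduces. A cut-off of 20 of 23 would give a type I error of 0.137, so 21 is the correct boundary.

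**2. Effect on the estimate** (Clopper-Pearson 95% intervals, no other TRSAEs):

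| First-dose TRSAEs | Reported after replacement | All treated subjects | Counted as failures, not replaced |
|---|---|---|---|
| 1 | 23/23 = 100% (85.2–100) | 23/24 = 95.8% (78.9–99.9) | 22/23 = 95.7% (78.1–99.9) |
| 2 | 23/23 = 100% (85.2–100) | 23/25 = 92.0% (74.0–99.0) | 21/23 = 91.3% (72.0–98.9) |

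**3. How often this would happen.** Enrol until 23 are retained. Let r be the number of TRSAE subjects removed and b the number retained. The trial completes if r + b ≤ 2, and each (r, b) has probability C(22+r, r) C(23, b) (qf)^r (q(1−f))^b (1−q)^(23−b). At q = 0.05, add the terms with r ≥ 1, in the order (1,0), (1,1), (2,0):

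- f = 1/8: 0.0442 + 0.0468 + 0.0033 = 0.094.
- f = 1/4: 0.0884 + 0.0802 + 0.0133 = 0.182.
- f = 1/2: 0.1767 + 0.1070 + 0.0530 = 0.337.

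**4. Effect on the test.** There are two readings of the three-subject count. In both, a removed subject is replaced up to the cap of two, and any later one is kept as a failure. Figures come from an exact recursion over enrolment.

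| f | Type I error, rule counts all treated | Power, rule counts all treated | Type I error, rule counts retained only |
|---|---|---|---|
| 1/8 | 0.047 | 89.2% | 0.079 |
| 1/4 | 0.045 | 88.9% | 0.113 |
| 1/2 | 0.040 | 88.4% | 0.175 |

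On the first reading the third TRSAE always stops the trial, so type I error falls slightly below the planned 0.049. On the second it rises. For example, 4 TRSAEs in 25 treated subjects, 2 of them replaced, would read 21/23 (one-sided p = 0.049, reject), whereas 21/25 gives p = 0.214.

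**The case against.** The strongest reply is that the authors did not mean this.

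- **Intent.** Section 11.3.2 reserves the two extra places for drop-out unrelated to treatment. Section 11.3.4.2 equates three TRSAE subjects with failure to reach 21 of 23, which works only if those subjects are among the 23. Section 9.1.1 keeps such subjects in follow-up.
- **Inference.** Section 11.3.3 says replaced, not excluded. Section 11.3.2 says non-evaluable subjects may be replaced, which is not the same as saying that every replaced subject is non-evaluable. A subject with a TRSAE has an observed primary outcome.
- **Size.** The first-dose share is assumed. At 1/12, the chance of completing the trial with an omitted TRSAE falls to about 6.4%. The phase I trial had no TRSAE in 10 subjects, and the number lost is capped at two.
- **Visibility.** SAE reporting under 12.3 to 12.5 is unaffected, and 11.3.1 already plans binomial estimates of treatment-related adverse events.

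Much of this stands. The exclusion is probably unintended, the event would remain visible in safety reporting, and the larger type I figures need a reading that goes against the plain wording of 11.3.4.2. The 3.4.2.4 route is weaker still, since that section has the subject go on to the next scheduled infusion, which cannot happen after a TRSAE.

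What does not stand is that intent settles the matter. The limit in 11.3.2 explains why the extra places exist, whereas 11.3.3 is mandatory and unqualified. A team applying it as written could remove a failure from the primary analysis without deviating from the protocol.

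**Conclusion.** The concern holds and should be fixed. As written, the replacement rule permits an outcome-dependent exclusion from the primary safety proportion. The damage is to the estimate and its interval. One or two omitted events would turn roughly 96% or 92% into 100%, and would raise the lower confidence limit from 78.9% or 74.0% to 85.2%. At the expected 5% TRSAE rate, the chance that the trial completes with at least one event omitted runs from about 9% to 34% as the assumed first-dose share goes from 1/8 to 1/2. The decision rule is safe provided the three-subject count includes every treated subject. Only if it does not would type I error reach 0.079 to 0.175 over the same range.

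The conclusion rests on reading 11.3.3 literally together with the link to evaluability in 11.3.2. Confidence is medium, because 11.3.2 points to a narrower intent.

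**What to change.** State in 11.3.2 and 11.3.3, with a matching line in 3.4.2.4:

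- A subject who receives any BMSC and has a TRSAE by day +56 is evaluable, counts as a failure for the primary endpoint and toward the three-subject rule in 11.3.4.2, and is not replaced.
- Replacement and non-evaluability apply only to subjects without a TRSAE.

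As a supportive analysis, report the TRSAE proportion among all treated subjects with its exact interval, and the number who left before day +56 without a TRSAE.

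The cost is one or two sentences in an amendment and one supportive table row. No extra patients are needed and no treatment rule changes. The design stays at 23 subjects, at least 21 of 23 for success, type I error 0.049 and power 89.5%.

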11.3.4 Stopping Rules

11.3.4.1 For Mortality

Any death occurring through the follow up period (3 weeks after last BMSC infusion) will halt further accrual irrespective of causality pending IRB review. The study will continue only with IRB determination that the event was not related to study procedures.

11.3.4.2 For Safety

The trial will be monitored for safety based on Treatment Related Serious Adverse Events (TRSAE), which is also the primary endpoint of the study. A TRSAE is defined as an SAE which is at least probably or definitely related to the BMSC infusions. The trial will be stopped if 3 subjects have developed one or more TRSAE's. This is based on the binomial test of the primary hypothesis (Section 11.3.2) and at least 21 of 23 subjects without a TRSAE are needed to reject the null hypothesis. If 3 or more subjects developed TRSAE's are observed, the null hypothesis will not be rejected and we will stop the study early.

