3.6 RESPONSE

Subjects will be assessed for response for the primary indication according to criteria listed in Appendix 2. The critical time points for response are at day +28 and day +56. Subjects are considered off protocol after 11 weeks of total enrollment. Subjects will receive additional infusions after day +28 based upon whether or not there is a complete response at the day +28 response assessment (Section 3.4.1). After coming off protocol, subjects will be followed for best response for up to 1 year on their parent transplant protocols.

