9.1.2 Completion of Infusions

A maximum of 12 infusions is planned. Final evaluation of outcomes and response to the BMSC will occur 3 weeks after the last infusion. After planned infusions and the three week monitoring period, subjects will be taken off protocol. Subjects will be followed for GVHD response and survival as a secondary endpoint for up to 1 year on their parent transplant protocol.

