11.2 Secondary Endpoints

Secondary endpoints for this study are:

- Proportions of complete response (CR), partial response (PR), mixed response (MR), no response (NR), and worsening disease (WD) among surviving patients at day +28 and +56 of study (Appendix 2). Need for secondary immunosuppression by day +28 and +56 of study. Steroid dose (prednisone equivalent) at day +28 and +56 of study. Proportion of responses in patients with high and low ST2 levels.

Secondary endpoints will not be used in assessing success or failure of the primary endpoint but are undertaken for descriptive or exploratory research and will be reported accordingly. The duration of treatment limiting toxicity monitoring will be 3 weeks after the last dose of BMSC. The total duration of treatment limiting toxicity monitoring will be 7-11 weeks. Total serious adverse event monitoring will continue until at least 3 weeks after the last dose of BMSC, and subjects experiencing adverse events related to BMSC will be monitored until toxicity resolution or stabilization.

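### Safety observation does not line up with the day +56 primary endpoint: it may end before day 56 for complete responders, and the stopping rule has no day limit

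*Combined protocol and SAP*

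**What the plan says.** **Endpoint and test.** Section 11.1 defines the primary endpoint as "The proportion of subjects reaching day +56 without a TRSAE". Section 11.3.2 tests that probability against 75% (one-sided 0.05, exact binomial, 23 subjects). It adds that "we expect 95% subjects would reach day +56 without a TRSAE" and states 89.5% power.

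**Stopping rule.** Section 11.3.4.2 monitors TRSAEs, "which is also the primary endpoint of the study", and stops the trial at three affected subjects. It bases this on the binomial test, which needs at least 21 of 23 subjects TRSAE-free. With three or more affected, "the null hypothesis will not be rejected and we will stop the study early". Neither the rule nor its definition of a TRSAE names a day.

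**Observation period.** Section 8.3: "The observational period for determining Treatment Limiting Toxicities is from the initiation of the BMSC infusion to 3 weeks after the last infusion". Section 11.2: "The total duration of treatment limiting toxicity monitoring will be 7-11 weeks".

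**Leaving the protocol.** Section 9.1.2: "After planned infusions and the three week monitoring period, subjects will be taken off protocol". After that it mentions follow-up for response and survival only, on the parent transplant protocol. Section 3.6 differs: "Subjects are considered off protocol after 11 weeks of total enrollment". The Appendix 3 calendar marks adverse events at each column through day 56, with no exception for subjects who stop at week 4.

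**Who is affected.** Under the protocol summary and 3.4.1, complete responders at week 4 receive no more infusions. All others receive four further weekly doses.

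**The concern.** Every subject should be observed over the interval that the primary endpoint covers, and a stopping rule said to follow from the primary test should count the same events as that test. Neither is assured here.

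For week-4 complete responders, the shortest written window closes before day 56. A TRSAE in the uncovered days might go unrecorded, and the subject would then count as TRSAE-free. That error favours the treatment, on a test where one subject separates rejection from non-rejection.

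For subjects dosed in weeks 5-8, the window runs past day 56. An undated count of three can then be reached while the day-56 test still rejects, so an unconditional statement in the plan is not always true.

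**Working it through.** **1. The plan's own figures.** With X the number TRSAE-free out of 23:
- P(X ≥ 21 | p = 0.75) = 0.0492, so 21/23 rejects.
- P(X ≥ 20 | p = 0.75) = 0.137, so 20/23 does not.
- P(X ≥ 21 | p = 0.95) = 0.8948, the stated 89.5%.

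The boundary and power are right.

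**2. When observation ends, counted from the first infusion.** Inputs: Tuesday/Friday dosing (3.4.1) and 21 days after the last infusion (8.3).
- *Complete responders.* Eight infusions span seven gaps alternating between 3 and 4 days, so infusion 8 falls on day 24-25. Adding 21 gives day 45-46; the 7 weeks in 11.2 give day 49. Shortfall: 56 − 49 = 7 to 56 − 45 = 11 days.
- *All others.* If weekly dosing starts on day 28-32, infusion 12 falls on day 49-53. Adding 21 gives day 70-74; 11 weeks give day 77. Excess over day 56: 14 to 21 days.

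**3. What the shortfall could cost (illustration).** Assumptions: constant TRSAE hazard; nothing recorded after a complete responder leaves; 71% complete responders, borrowed from the de novo study in 2.4.2. None of these is established for this trial.
- If the true day-56 rate is 95%, a complete responder event-free on leaving has a chance of a missed first TRSAE of 1 − 0.95^(7/56) = 0.6% to 1 − 0.95^(11/56) = 1.0%.
- If the true rate is 75%, the recorded TRSAE-free probability with exit at day 49 is 0.71 × 0.75^(49/56) + 0.29 × 0.75 = 0.71 × 0.7775 + 0.2175 = 0.7695, and P(X ≥ 21) = 0.074. With exit at day 45 it is 0.71 × 0.7936 + 0.2175 = 0.7810, and P(X ≥ 21) = 0.093.

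So the false-positive rate would be 7.4-9.3% instead of 4.9%. This is a worst case, because it assumes that the calendar is not followed.

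**4. Counterexample for the stopping sentence.** Two subjects have a TRSAE by day 56, and a third has a first TRSAE between day 57 and day 77. The undated count is 3, so the trial stops. TRSAE-free at day 56: 23 − 2 = 21, p = 0.0492, H0 rejected. If only TRSAEs by day 56 count, three affected subjects leave at most 20/23 (p = 0.137) and the sentence is exactly true.

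**5. How likely the conflict is.** The documents give no late rate. Assume that the hazard giving 95% at day 56 continues. The late rate for a subject followed to day D is 1 − 0.95^((D−56)/56): 1.3% at D = 70 and 1.9% at D = 77. Multiply by (1 − complete-response share) to get r. Then P(conflict) = Σ over k = 0, 1, 2 of P(k early | 23, 0.05) × P(at least 3 − k late | 23 − k, r).

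| Complete-response share | P(conflict), all 23 followed |
|---|---|
| 71% (2.4.2) | 1.7-2.6% |
| 26-60% (2.2.1, other drugs plus steroids) | 2.4-7.1% |
| 0%, all followed to day 77 | 9.9% |

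These figures include cases where the third event comes during accrual. The question is then whether to stop or continue, and no 23-subject test exists. In a simulation with the same hazard and 23 subjects accrued evenly over 12-18 months, the third event came after the last enrolment with probability 0.4-0.9% at 71% complete response and 2.4-3.2% in the extreme case. A higher late hazard gives more: with 5% affected by day 56 and a further 5% of all subjects late, the first calculation gives 30.3%.

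**The case against.** On the stopping rule, the natural reading shows no conflict. The text identifies the TRSAE with the primary endpoint and rests the rule on the primary test, and both are limited to day 56. The mortality rule in 11.3.4.1 writes out a three-week window, while 11.3.4.2 does not. This objection largely stands and reduces the second part to a wording fault. It does not remove it, because the rule and the TRSAE definition carry no date, and 8.3 repeats that definition under an observation period running past day 56.

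On complete responders, 11.2 continues serious adverse event monitoring until at least three weeks after the last dose, which is a minimum. Section 3.6 gives 11 weeks, 3.7 assesses survival at day +56, and the calendar records adverse events through that date. So a reader might infer that complete responders will be lost before the endpoint, but the documents do not support that. They support only that some passages permit it and others exclude it.

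Three other stronger readings also fail:
- *Late TRSAEs are lost.* They are monitored under 11.2, and 11.3.1 plans a time-to-event analysis.
- *The mismatch lets an unsafe product pass.* It runs the other way: a late event can stop a trial that the day-56 test would call a success.
- *Success needs a second, full-window criterion.* A day-56 landmark is a legitimate choice. Under the hazard assumed above, the extra criterion would cut the chance of success from 89.5% to 86.9-87.8% at 71% complete response, and to 79.6% with none.

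The origin of day +56 is a lesser matter. The summary counts from diagnosis and 11.2 from study, but both phrases concern responses. Section 8.3 starts toxicity observation at the infusion, and 7.1.1 and the calendar footnote put day 0 just before it. Section 11.1 itself names no origin.

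**Conclusion.** The concern holds in two parts of unequal weight.

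The firmer part is the contradiction on the primary endpoint. Sections 8.3, 9.1.2 and the seven-week figure in 11.2 allow observation of complete responders to end 7-11 days before day 56, against 3.6 and the calendar. This follows from the text and the dosing schedule. The 7.4-9.3% false-positive illustration rests on assumed inputs and on nothing being recorded after exit.

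The second part is a small wording fault: read literally, the sentence about the null hypothesis fails for two early TRSAE subjects plus one late. Its probability is probably low, but 9.9% is not a ceiling, since every figure depends on an assumed late hazard. The conflict cannot create a false declaration of safety if the stopping text is followed.

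The sample size, boundary and power calculation are correct.

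**What to change.** 1. Reconcile 8.3, 9.1.2 and 11.2 with 3.6 and the calendar so that TRSAE ascertainment reaches at least day 56 for every subject, whenever infusions end. Relative to 9.1.2 this adds 7-11 days for complete responders, at visits already in the calendar.
2. In 11.3.4.2, do one of two things: limit the statement about the null hypothesis to TRSAEs by day +56, or keep the longer safety window for stopping and delete the claim about the test. Either removes the mismatch. No second success criterion is needed.
3. Report the TRSAE-free proportion over the full monitoring window next to the day-56 proportion, with the Kaplan-Meier analysis already planned in 11.3.1.
4. Minor: name one origin for day +56 in 11.1 and align the summary, 11.2, 7.1.1 and the calendar footnote with it.

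The cost is amendment wording. N = 23, the 21/23 boundary, alpha 0.049 and 89.5% power for the day-56 test stay as they are.
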